5.7.3 Exploratory Endpoint

An exploratory endpoint of this study is the descriptive efficacy of *Wilate* in surgical prophylaxis (for details see section 5.9).

5.8 Pharmacokinetics / Pharmacodynamics

For Pharmacokinetics and IVR assessments FVIII:C will be measured by both, the chromogenic (CHR) and one-stage assay (OS) and analyzed based on actual IMP potency (refer to section 8.1).

The PK profiles of *Wilate* and the PK parameters derived from them will be summarized by descriptive statistics as well as the presentation of concentration vs. time plots based on the PK set. In the analysis of the PK profiles geometric means and standard deviations will be presented in addition to the arithmetic means and standard deviations.

The following PK parameter will be derived and presented using a non-compartment model:

- Area under the curve (AUC) and AUC normalized for the administered dose (AUC_{norm})
- FVIII in vivo half-life ($T_{1/2}$)
- Maximum plasma concentration (C_{max})
- Time to reach maximum plasma concentration (T_{max})
- Mean residence time (MRT)
- Volume of distribution (Vd)
- Clearance (CL)
- Incremental in vivo recovery (IVR)

Analysis of variance (ANOVA) will be used in an exploratory sense to assess a possible association between ABO blood type, VWF:Ag, and the FVIII:C half-life of *Wilate*.

Incremental IVR will be calculated from FVIII:C plasma levels measured before injection and peak levels obtained in the 15-min post-injection sample using actual IMP potencies. The results of the IVR assessments over time will be analyzed in summary tables for each time point and their differences to baseline along with 95% CIs for the mean differences.

5.9 Surgeries

Efficacy in surgical prophylaxis will be analyzed descriptively, presenting summary tables and listing on all aspects of surgical treatment and procedures as well as efficacy ratings.

| | |
|---|---------------|
| 
STATISTICAL ANALYSIS PLAN Protocol No: WIL-30
 | |
| Version Number: 1.2 | Page 21 of 27 |
| Date of Issue: 2019-07-08 | |

The following surgery-related parameters will be presented:

- Number of minor and major surgeries
- Location, severity (minor or major, for definitions see protocol), and type (planned or emergency) of surgery
- Expected and actual duration of surgical procedure
- Expected and actual blood loss
- Pre-, intra-, and/or postoperative IMP administration data (only listed)
- Pre-, intra-, and postoperative FVIII plasma levels (only listed)
- VWF:Ag and VWF:Ac (descriptive statistics including changes to pre-infusion)
- Frequency and amount of blood transfusion requirements
- Presence of wound hematomas and whether or not they require surgical evacuation (only listed)
- Assessment of efficacy of surgical prophylaxis:
 1. at the end of surgery by the surgeon
 2. at end of the postoperative period by the hematologist
 3. Overall efficacy taking both the intra- and postoperative assessments into account assessed by the Investigator.
- Number of successively treated surgeries ('excellent' or 'good' overall efficacy rating)
- Concomitantly administered products (only listed)
- Narrative describing the outcome and efficacy of the intervention (only listed)
- Inhibitor testing (within 3–8 weeks after the end of the surgery, this visit may coincide with another study visit with scheduled inhibitor testing)

5.10 Safety

All safety analyses will be based on the SAF population.

The analysis of safety will include the occurrence of AEs, the results of the safety laboratory tests, immunogenicity measurements and the occurrence of parvovirus B19 seroconversions.

5.10.1 Adverse events

Adverse events (AEs) will be coded by the CRO according to the latest Medical Dictionary for Regulatory Activities (MedDRA). Coding will be agreed upon with the Sponsor before database lock (cf. DMP).

All adverse events recorded since signing of the informed consent form (ICF) will be listed in appendix 16.2 of the report differentiating by treatment emergent and non-treatment emergent events. This includes also post-study serious adverse events (SAEs) which occurred up to 4

| | |
|--|---------------|
| 
STATISTICAL ANALYSIS PLAN Protocol No: WIL-30
 | |
| Version Number: 1.2 | Page 22 of 27 |
| Date of Issue: 2019-07-08 | |

weeks after the last IMP administration (not monitored proactively), thromboembolic events monitored proactively by performing a Follow-up Contact 30 days after the completion visit as well as safety relevant information on drug overdosing, drug interactions and medication errors.

The analysis will include only treatment-emergent adverse events (TEAEs), i.e. all documented AEs that started or worsened after the start of IMP infusion. It is assumed that for each increase in intensity of an AE a new entry of the AE will be done by the investigator; hence such cases will be analyzed like different phases of the same AE.

A descriptive analysis will be performed. Incidences will be presented by primary system organ classes (SOC) and incidences of PT within primary SOC sorted according to the Internationally Agreed Order.

Multiple counts within a PT or SOC (repeated or different included terms or changes in descriptors) will be counted only once for the calculation of incidences.

Global incidences will be calculated for:

- All TEAE irrespective of the causality assessment
- Related TEAEs ('Probably' or 'Possible')
- TEAEs by worst severity
- Serious TEAEs

A listing of "special cases" containing subject identification, age, sex, AE descriptors, start and end of treatment will be prepared for the following types of TEAEs:

- Serious adverse events (SAE)
- Adverse events which led to death
- Adverse events which led to discontinuation

Serious non-treatment emergent AEs will be listed separately.

5.10.2 Vital signs

Vital signs parameters (systolic/diastolic blood pressure, pulse, body weight, respiratory rates, body temperature) will be assessed at screening, PK visit, after 3 months at study completion visits and during surgery.

Descriptive analyses of values will be performed and changes from baseline will be analyzed for vital signs parameters at visits.

| | |
|---|---------------|
| 
STATISTICAL ANALYSIS PLAN Protocol No: WIL-30
 | |
| Version Number: 1.2 | Page 23 of 27 |
| Date of Issue: 2019-07-08 | |

5.10.3 Safety laboratory variables

The analysis of the safety parameters (lab values for Hematology and Clinical chemistry) recorded during visits (screening, PK visit, 3-month and study completion visits) and at surgery will be purely descriptive and presented as summary tables or listings.

Time profiles of the safety laboratory parameters will be analyzed by presenting sampling statistics for the values as well as their difference to baseline at each time point. Additionally, frequency tables for values outside the normal ranges will be presented.

Similarly, time profiles of FVIII inhibitor testing results will be analyzed by presenting sampling statistics for the values as well as frequency tables for positive findings, along with 95% Pearson-Clopper CIs.

The thromboembolic risk will be monitored by determination of VWF:Ag and VWF:Ac during the study and especially postoperatively. Descriptive statistics including changes to pre-infusion will be presented by visit and timepoint (with 95% CI) for visits or by operative day and timepoint for surgeries, respectively.

To assess the viral safety of *Wilate* incidences of parvovirus B19 seroconversions between baseline and end of study will be estimated along with 95% Pearson-Clopper CIs.

5.10.4 Other safety variables

Other safety parameters (e.g., changes in physical examination findings) will be analyzed by summary tables or listings. All abnormal findings from the physical examination will be listed.

The analysis of the safety parameters recorded during surgery (lab values) will be purely descriptive and presented as summary tables or listings.

5.11 Other variables

Not applicable.

5.12 Interim analyses

Not applicable.

6 QUALITY CONTROL

The responsible project manager will review the SAP before it is provided to the Sponsor for review. The SAP will be signed off only when approval from the Sponsor's representative is received.

STATISTICAL ANALYSIS PLAN

Protocol No: WIL-30

Version Number: 1.2

Date of Issue: 2019-07-08

Page 24 of 27

Log files of all SAS® programs needed for analysis will be checked for errors, warnings and suspicious notes by the statistical programmer. All findings will be either eliminated or commented upon. The final version of each program will be stored along with its log file in the electronic archive.

All programs will be validated by the author.

The agreement of the program outputs with the SAP, their consistency and plausibility will be checked by the TS. Moreover, the TS will review the outputs regarding completeness, readability and comprehensibility.

8 APPENDICES

8.1 Formulas for derived variables

| Variable | Description |
|---|--|
| Actual potency | Potency of IMP (IU) based on central laboratory measurements of FVIII content by two assay methods: CHR (chromogenic) and OS (one-stage). The analysis of PK and IVR assessment will be based on actual potencies |
| Durations between two dates | Later date minus earlier date plus 1, expressed in days. (Remark: Duration will be 1, if both dates are the same.) |
| Spontaneous annualized bleeding rate (SABR) | Number of spontaneous bleedings (excluding bleedings occurring in surgery periods) between first dose of IMP and Study Completion visit (or last dose of IMP in case completion visit not performed) / time under prophylaxis (days)/365.25 (see prophylactic treatment phase) |
| Total annualized bleeding rate (TABR) | Number of bleedings (excluding bleedings occurring in surgery periods) between first dose of IMP and Study Completion visit (or last dose of IMP in case completion visit not performed) / time under prophylaxis (days)/365.25 (see prophylactic treatment phase) |
| Surgery Phase | Last treatment for surgery – first treatment for surgery + 1 |
| Prophylactic treatment phase | Date of completion visit or date of last treatment with IMP in case completion visit not performed) – (date of first prophylactic treatment after the PK visit) + 1 – Surgery phases |
| Time in study | Date of study completion – date of screening +1 |

| STATISTICAL ANALYSIS PLAN Protocol No: WIL-30 | |
|--|---------------|
| Version Number: 1.2 | Page 25 of 27 |
| Date of Issue: 2019-07-08 | |

| Variable | Description |
|---|---|
| Time under treatment | Date of last treatment – date of first treatment + 1 (average drug consumption data will be calculated relative to time under treatment) |
| AUC | Area under the curve from baseline to infinity $AUC = \sum \left(\frac{(C_n + C_{n+1})}{2} \cdot \Delta t \right) + \frac{C_{last}}{K}$ (C_{last} is the last available measurement) |
| AUC _{norm} | AUC normalized for the administered dose |
| AUMC | Area under the moment curve (from baseline to infinity) $AUMC = \sum \left(\frac{(t_n \cdot C_n + t_{n+1} \cdot C_{n+1})}{2} \cdot \Delta t \right) + \frac{C_{last} \cdot t_{last}}{K^2} + \frac{C_{last}}{K}$ |
| CL | Clearance $CL = \frac{D}{AUC}$ where D is the actual dose administered (see remark above) |
| C ₀ | FVIII concentration before IMP administration |
| C _{max} | Maximal measured concentration after end of IMP infusion (peak concentration) |
| ED | Exposure day = each calendar day the subject received IMP |
| Incremental recovery (IVR) | $IVR = \frac{(C_{max} - C_0) \cdot BW}{D}$ where BW stands for the body weight in kg and D is the dose according to the actual potency of the FVIII concentrate as described in above |
| Labelled potency | Potency of IMP (IU) based on label of vial (IU). Dosing analyses will be based on labelled potency |
| MRT | Mean residence time $MRT = \frac{AUMC}{AUC}$ |
| Success (for bleeding episodes and surgeries) | Excellent or good efficacy rating |

| | |
|----------------------------------|---------------|
| STATISTICAL ANALYSIS PLAN | |
| Protocol No: WIL-30 | |
| Version Number: 1.2 | Page 26 of 27 |
| Date of Issue: 2019-07-08 | |

| Variable | Description |
|-----------|--|
| $T_{1/2}$ | In vivo half-life using linear regression on the terminal phase of the logarithm of the concentration; $T_{1/2} = \frac{\ln(2)}{K}$ (where K , the elimination rate constant, is determined as the slope of the regression line) |
| T_{max} | Time to reach maximum plasma concentration (Timing starts at end of infusion) |
| Vd | Volume of distribution $Vd = CL \cdot MRT$ |

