3.1.2 Secondary Endpoints

The secondary endpoints of this study are the:

- 1. Total annualized bleeding rate (TABR)
 - TABR will be calculated as the total number of BEs in the time period between first dose of IMP and the Study Completion Visit, divided by the duration (in years) between first dose of IMP and the Study Completion Visit. Surgery periods, and BEs occurring within these periods, will be excluded from the calculation of TABR.
- 2. Spontaneous annualized bleeding rate (SABR), calculated in analogy with TABR
- 3. Efficacy of *Wilate* in the treatment of breakthrough BEs based on the proportion of BEs successfully treated with *Wilate*
- 4. Wilate consumption data (FVIII IU/kg per week per patient) for prophylaxis
- 5. Incremental IVR of *Wilate* over time (at baseline, and at 3 and 6 months of treatment)
- 6. Association between AB0 blood type and the FVIII:C half-life of Wilate
- 7. Association between VWF:Ag concentration and the FVIII:C half-life of Wilate
- 8. Safety and tolerability of *Wilate* by monitoring adverse events (AEs) throughout the study
- 9. Immunogenicity of *Wilate* by testing for FVIII inhibitors
- 10. Virus safety in terms of parvovirus B19

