6.1.6 Study Completion (6-Month) Visit

The Study Completion Visit will take place 6 months (+2 weeks) after the start of the Prophylactic Treatment Phase.

A prophylactic injection of *Wilate* will be administered, if possible after a washout period of at least 48 hours from the patient's latest FVIII injection. Patients must not be experiencing any bleeding.

The following assessments will be performed:

- Review of patient diary
- Body weight before injection
- Blood samples will be taken for the following purposes and at the following time points:
 - FVIII:C plasma concentration (OS and CHR) for IVR assessment within 1 h
 before injection of the last prophylactic dose and 15±5 min after the end of the injection
 - Safety laboratory before and 15±5 minutes after injection
 - **FVIII inhibitor** before injection
 - Plasma VWF:Ag and VWF:Ac within 1 h before injection and 15±5 min after the end of injection
 - Parvovirus B19 antibodies before injection, if first sample was negative
- Vital signs before and 15±5 min after the end of injection
- AE monitoring
- Concomitant medication
- Physical examination

All used and unused IMP vials will be returned by the patient.

Patients prematurely withdrawing from the study for any reason will also be invited to attend the Study Completion Visit.

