8 APPENDICES

8.1 Formulas for derived variables

| Variable | Description |
|-----------------------------|--|
| Actual potency | Potency of IMP (IU) based on central laboratory measurements of FVIII content by two assay methods: CHR (chromogenic) and OS (one-stage). The analysis of PK and IVR assessment will be based on actual potencies |
| Durations between two dates | Later date minus earlier date plus 1, expressed in days. (Remark: Duration will be 1, if both dates are the same.) |
| Annual bleeding rate | Number of bleeding / (last date of IMP – first date of IMP + 1)/365.25 |
| AUC | Area under the curve from baseline to infinity $AUC = \sum \left(\frac{(C_n + C_{n+1})}{2} \cdot \Delta t \right) + \frac{C_{last}}{K}$ (C_{last} is the last available measurement) |
| AUC _{norm} | AUC normalized for the administered dose |
| AUMC | Area under the moment curve (from baseline to infinity) $AUMC = \sum \left(\frac{(t_n \cdot C_n + t_{n+1} \cdot C_{n+1})}{2} \cdot \Delta t \right) + \frac{C_{last} \cdot t_{last}}{K^2} + \frac{C_{last}}{K}$ |
| CL | Clearance $CL = \frac{D}{AUC}$ where D is the actual dose administered (see remark above) |
| C_0 | FVIII concentration before IMP administration |
| C_{max} | Maximal measured concentration after end of IMP infusion (peak concentration) |
| ED | Exposure day = each calendar day the subject received IMP |
| Incremental recovery (IVR) | $IVR = \frac{(C_{max} - C_0) \cdot BW}{D}$ where BW stands for the body weight in kg and D is the dose according to the actual potency of the FVIII concentrate as described in above |
| Labelled potency | Potency of IMP (IU) based on label of vial (IU). |

STATISTICAL ANALYSIS PLAN

Protocol No: WIL-30

Version Number: 1.0

Date of Issue: 2017-04-26

Page 25 of 27

| | |
|---|--|
| | Dosing analyses will be based on labelled potency |
| MRT | Mean residence time $MRT = \frac{AUMC}{AUC}$ |
| Success (for bleeding episodes and surgeries) | Excellent or good efficacy rating |
| T _{1/2} | In vivo half-life using linear regression on the terminal phase of the logarithm of the concentration; $T_{1/2} = \frac{\ln(2)}{K}$ (where K , the elimination rate constant, is determined as the slope of the regression line) |
| T _{max} | Time to reach maximum plasma concentration (Timing starts at end of infusion) |
| Vd | Volume of distribution $Vd = CL \cdot MRT$ |

| | |
|--|---------------|
| STATISTICAL ANALYSIS PLAN Protocol No: WIL-30 | |

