2.5 Planned sample size

Overall, 10 PTPs (5 patients aged 1 to <6 years of age and 5 patients aged 6 to <12 years) will be enrolled into this study. The aim is to obtain evaluable data on 8 patients who complete both the 2-day PK Phase and the 6-month Prophylactic Treatment Phase. Of the 8 evaluable patients, 4 patients must be 1 to <6 years of age, and another 4 patients must be 6 to <12 years of age. Enrolled patients will be replaced only if they do not complete the PK assessment.

The sample size of 10 pediatric patients to be enrolled was based on medical and regulatory reasoning. No statistical sample size estimation was performed.

| | |
|---|---------------|
| 
STATISTICAL ANALYSIS PLAN Protocol No: WIL-30
 | |
| Version Number: 1.2 | Page 14 of 27 |
| Date of Issue: 2019-07-08 | |

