5 STATISTICAL ANALYSES

All statistical analyses will be performed using SAS[®] for Windows (Version 9.3 or later).

Descriptive statistics will always be given for the entire population.

| | |
|---|---------------|
| 
STATISTICAL ANALYSIS PLAN Protocol No: WIL-30
 | |
| Version Number: 1.2 | Page 16 of 27 |
| Date of Issue: 2019-07-08 | |

The analysis of safety will be based on the SAF set.

Analysis of the PK properties of *Wilate* will be based on the PK set.

For secondary endpoints, FAS and PP analyses will be carried out, unless these analysis sets differ by no more than 1 patient from the FAS.

Analysis of the efficacy and safety of *Wilate* in surgeries will be based on the SURG set.

If not stated otherwise the following standard descriptive statistics will be presented:

Descriptive statistics for continuous data

Number of subjects (N), arithmetic mean, standard deviation (SD), minimum, lower quartile, median, upper quartile and maximum will be presented. Usually mean and quartiles will have 1 decimal more, SD 2 decimals more than the original values (as given with min, max); N has no decimals. These descriptive statistics will be determined for measured values and for differences to baseline.

Descriptive statistics for categorical data

Absolute frequencies (N) will be presented with 0, relative frequencies (%) with 1 decimal. For changes from baseline, shift tables may be generated.

Inferential statistics

If not stated otherwise all statistical tests will be performed as described in the corresponding sections below.

All p-values will be rounded to 4 decimals (p<0.0001 will be displayed, if the p-values are less than 0.0001). Statistical significance will be declared if the rounded p-value will be less than 0.05.

All confidence intervals (CI) will be derived two-sided and at a confidence probability of 1- α = 0.95.

Listings

All subject data will be listed by subject. Identification variable will be the subject ID (composed of study, center and subject number separated by a hyphen, e.g. '30-01-01'). Any derived data listed will also be stored permanently and will be calculated as outlined in section 8.1 of this SAP.

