5.7.2 Efficacy

All efficacy variables will be analyzed based on the FAS and additionally on the PP set, unless these analysis sets are identical.

Efficacy endpoints are:

- Efficacy of prophylactic treatment with *Wilate* based on the total annualized bleeding rate (TABR) as well as the spontaneous annualized bleeding rate (SABR)
- Efficacy of *Wilate* in the treatment of breakthrough BEs based on the proportion of BEs successfully treated with *Wilate* (successfully includes efficacy ratings assessed as either ‘excellent’ or ‘good’)
- *Wilate* consumption data (FVIII IU/kg per week and per month per subject) for prophylaxis
- Incremental IVR of *Wilate* over time (at baseline, and at 3 and 6 months of treatment) (refer to section 5.8)

Efficacy of Prophylactic Treatment with Wilate

The analysis of the efficacy of prophylactic treatment with *Wilate* will be statistically evaluated by presenting descriptive sampling statistics for the TABR and SABR, along with an exploratory 95% CI for the mean. TABR and SABR will be calculated as the total number of BEs or total number of spontaneous BEs, respectively, in the time period between first dose of IMP and the study completion visit, divided by the duration (in years) between first dose of IMP and the study completion visit. Surgery periods, and BEs occurring within these periods, will be excluded from the calculation of annual bleeding rates

Efficacy in the Treatment of Breakthrough BEs

To assess the hemostatic efficacy of *Wilate* in the treatment of breakthrough bleedings, a frequency distribution of all such BEs being successfully treated will be presented, along with an exploratory 95% CI.

Primarily, all obtained data on treatment characteristics (IMP dosages, frequencies, total consumption) and BEs (duration, frequency, efficacy assessment) will be described by providing summary statistics.

In general, the efficacy of bleeding episodes will also be presented by type (spontaneous, traumatic, postoperative, other), sites (nose, oral cavity, knee, ankle, elbow, arm, leg, intestinal and other. In addition, knee, ankle and elbow sites will be summarized as site ‘joint’) and severity (minor, moderate, major, life-threatening).

| | |
|--|---------------|
| STATISTICAL ANALYSIS PLAN Protocol No: WIL-30 | |
| Version Number: 1.2 | Page 20 of 27 |
| Date of Issue: 2019-07-08 | |

Analysis of Other Secondary Endpoints

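### SAP 8.1 omits a bracket in the TABR and SABR formulas, and the same rows count bleeds and time over different windows

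*SAP*

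**What the plan says.** SAP v1.2, section 8.1, has one row for SABR and one for TABR. Each puts a number of bleedings, excluding those in surgery periods, over "time under prophylaxis (days)/365.25 (see prophylactic treatment phase". The same table expresses durations in days: "Later date minus earlier date plus 1, expressed in days".

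The prose definition is different. SAP 5.7.2 says the count is "divided by the duration (in years) between first dose of IMP and the study completion visit". Protocol 3.1.2 says the same of TABR, "divided by the duration (in years) between first dose of IMP and the Study Completion Visit", and defines SABR by analogy. Both exclude surgery periods.

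On the standing of 8.1, the Listings paragraph of SAP section 5 says that listed derived data "will be calculated as outlined in section 8.1 of this SAP". SAP 3.2 states that no deviations from the protocol are planned.

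On the window, the 8.1 rows count bleeds from the first dose of IMP. The time they refer to, the prophylactic treatment phase, begins in 8.1 at the first prophylactic treatment after the PK visit. SAP 5.7.2 and Protocol 3.1.2 start both count and time at the first dose of IMP.

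**The concern.** TABR and SABR are secondary endpoints 1 and 2, and the plan judges prophylactic efficacy by them. Section 8.1 is where a programmer looks for the derivation. With ordinary left-to-right precedence, which SAS also uses, the printed expression is count/(days × 365.25), not count/(days/365.25). A program that follows 8.1 literally is wrong, and a correct program does not match 8.1. SAP section 6 has programs validated by their own authors and has the trial statistician check outputs for agreement with the SAP. The text used for that check should therefore be right.

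The window mismatch is much smaller, but it would not stand out. It produces plausible rates that differ slightly from those the protocol defines.

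**Working it through.** **Inputs.** The factor 365.25 is from SAP 8.1. Follow-up is from Protocol 6.1.6: "The Study Completion Visit will take place 6 months (+2 weeks) after the start of the Prophylactic Treatment Phase". I take this as D = 183 days, or 183 + 14 = 197 days at the upper end of the window; the conversion of 6 months to 183 days is an assumption. Bleed counts N are illustrative, because the documents state no bleeding rate and there is no planned figure to reproduce.

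**Step 1, formulas.**
- As printed: N / D / 365.25 = N / (D × 365.25).
- As defined in SAP 5.7.2 and Protocol 3.1.2: N / (D / 365.25) = N × 365.25 / D.

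**Step 2, worked example.** For N = 3 and D = 183:
- Printed: 3 / 183 / 365.25 = 0.016393 / 365.25 = 0.000045.
- Defined: 183 / 365.25 = 0.5010 years, and 3 / 0.5010 = 5.99 per year.

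**Step 3, other values.**

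| Bleeds | Days | As printed | As defined (per year) |
|---|---|---|---|
| 1 | 183 | 0.0000150 | 2.00 |
| 5 | 183 | 0.0000748 | 9.98 |
| 1 | 197 | 0.0000139 | 1.85 |
| 5 | 197 | 0.0000695 | 9.27 |

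**Step 4, ratio.** (N × 365.25 / D) ÷ (N / (D × 365.25)) = 365.25² = 133,407.6. It does not depend on the count or the follow-up.

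**Step 5, is it a text-extraction artefact?** Unlikely. SAP v1.0 and v1.1 print "Number of bleeding / (last date of IMP – first date of IMP + 1)/365.25", where the bracket closes before the division by 365.25. Other brackets in the v1.2 rows survived, and the fractions for CL, MRT and IVR in the same table were read as fractions.

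**Step 6, the window.** Let g be the days from the PK dose, which is the first IMP dose, to the first prophylactic dose. With 183 days from the first prophylactic dose to completion and no surgery, 8.1 divides by 183 days, and 5.7.2 by 183 + g. For the same count, the 8.1 rate is higher by the factor (183 + g) / 183:
- g = 2: 185 / 183 = 1.011
- g = 7: 190 / 183 = 1.038
- g = 14: 197 / 183 = 1.077

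Two days is about the least possible, since PK sampling runs to 48 ± 2 hours (Protocol 6.1.2). The upper value of 14 days is an assumption. Adding the bracket does not change this factor.

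**The case against.** The strongest reply is that the intended meaning is not in doubt. The rows are labelled as annualized rates, 365.25 has no purpose except to turn days into years, and 5.7.2 and Protocol 3.1.2 give the definition in words. The rows are verbal descriptions rather than code. The first slash is spaced and the second is not, which hints at the right grouping, and bracketing in this table is loose elsewhere: the prophylactic treatment phase row has an unmatched closing bracket. The sentence in section 5 concerns listed derived data and does not say that 8.1 overrides 5.7.2. Section 6 has the trial statistician check outputs for consistency and plausibility, and rates near 0.00001 beside bleed counts for about ten children would be conspicuous. The endpoints are secondary and descriptive, and no sample size rests on them ("No statistical sample size estimation was performed").

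All of this stands as to consequence. A reader might infer that the trial's bleeding rates will be reported as near zero, or that they cannot be reproduced from the SAP. The documents support neither inference. They state no rate that is wrong, 5.7.2 supplies the correct unit conversion, and the factor of 133,400 describes a hypothetical literal evaluation. Its size makes a slip easier to detect and is not a measure of likely bias.

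The reply does not make the printed rows correct, and it does not touch the window mismatch, which would pass a plausibility check.

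**Conclusion.** The TABR and SABR rows in SAP v1.2 section 8.1 are wrong as written and conflict with SAP 5.7.2 and Protocol 3.1.2. The missing bracket is a notation error. Evaluated literally, it understates the rate by a factor of 365.25², about 133,400, whatever the data. The practical risk to reported results is low, because the intent is recoverable and the error would be obvious in output.

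The differing windows for count and time are a second, smaller inconsistency in the same rows, worth about 1% to 8% of a rate for a given count. That range assumes a gap of 2 to 14 days, 183 days of prophylaxis and no surgery. Both are worth correcting, since 8.1 is the derivation reference for two named secondary endpoints.

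**What to change.** Restate both rows as: number of bleedings / (days at risk / 365.25), or equivalently number of bleedings × 365.25 / days at risk.

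In the same edit, define days at risk once and apply it to both count and time. The window already in 5.7.2 and Protocol 3.1.2 runs from the first dose of IMP to the Study Completion Visit, less surgery periods. Using it keeps the statement in SAP 3.2 true. The existing 8.1 rule for patients without a completion visit, which ends at the last IMP dose, can stay, since it already applies to both. If the sponsor prefers to start at the first prophylactic treatment, the bleed count should start there too, and the change should be recorded in SAP 3.2 as a departure from the protocol.

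The cost is a wording change in two rows of the SAP and a check that the program matches. No new data are needed. The bracket changes no estimand, and using the protocol window restores the rate that the protocol defines.
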